Note: There must be at least 7 days between Visit 1 (Screening) and Visit 2 (Day 1).

Table 5: Period 1 Schedule of Assessments – 14-Week Treatment Period

| Study Procedures | 14-Week Treatment Period 1 Visit Schedule | | | Taper Period, If Applicable | | Study Visit Week 16 or Week 17 for AED Patients Tapering Study Drug ^a | Un- scheduled Visit(s) | Week 10 Telephone Follow-up |
|---|--|-------------------|---|--|------------|---|------------------------------|-----------------------------------|
| | Visit 2 | Visit 3 Week 6 | Visit 4 Week 14 EOS/ET ^a | Week 15 | Week 16 | | | |
| | Day 1 | (± 3 days) | (± 3 days) | (± 3 days) | (± 3 days) | | | |
| | Study Drug Dosing | | | Tapered 50% each week. No Study Visit | | | | |
| Review Eligibility Criteria | X | | | | | | | |
| Concomitant Medications | X | X | X | | | X | X | X |
| Physical/Neurological Exam ^b | X | X | X | | | X | | |
| Vital Signs ^c | X | X | X | | | X | X | |
| 12-lead ECG ^d | X | X | X | | | | | |
| Laboratory Tests and Urinalysis | | X | X | | | | | |
| Pregnancy Test ^e | | X | X | | | X | | |
| CBD/THC PK Blood Sample | | X | X | | | | | |
| Blood Sample Valproic Acid ^f | | X | X | | | | | |
| ABC-C | X | X | X | | | | | |
| CGI-S | X | X | X | | | | | |
| CGI-I | | X | X | | | | | |
| ADAMS | X | X | X | | | | | |

Table 5: Period 1 Schedule of Assessments – 14-Week Treatment Period, cont'd

| Study Procedures | 14-Week Treatment Period – Visit Schedule | | | Taper Period, If Applicable | | Study Visit Week 16 or Week 17 for AED Patients Tapering Study Drug ^a Visit ^a | Un- scheduled Visit(s) | Week 10 Telephone Follow- up ^l |
|---|---|-------------------------------------|---|--|---------------------------|--|------------------------------|--|
| | | | | | | | | |
| | Visit 2 Day 1 | Visit 3 Week 6 (± 3 days) | Visit 4 Week 14 EOS/ET ^a (± 3 days) | Week 15 (± 3 days) | Week 16 (± 3 days) | | | |
| | Study Drug Dosing | | | Tapered 50% each week. No Study Visit | | | | |
| C-SSRS | X | X | X | | | X | X | |
| Qualitative Caregiver Behavioral Problems/Improvements Survey | | X | X | | | | | |
| Children’s Sleep Habit Questionnaire | | | X | | | | | |
| Pediatric Anxiety Rating Scale - Revised | X | X | X | | | | | |
| Instruct Parent/caregiver on Study Drug Application ^g | X | | | | | | | |
| Daily Study Drug Application ^h | X | X | X | X | X | | | |
| Skin Assessment Exam ⁱ | X | | | | | | | |

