| Pregnancy Test ^d | | | X | | | X | |
| CBD/THC PK Blood Sample | | | X | | | | |
| Blood Sample for Valproic Acid ^{e, g} | | | X | | | | |
| ABC-C | X | X | X | | | | |
| CGI-S | X | X | X | | | | |
| CGI-I | X | X | X | | | | |
| ADAMS | X | X | X | | | | |

Table 6: Period 2 Schedule of Assessments – 24-Week Extension Treatment Period, cont'd

| Study Procedures | 24-Week Treatment Period – Visit Schedule | | | Taper Period, If Applicable | | Study Visit Week 40 or Week 41 for AED Patients Tapering Study Drug ^a Visit ^a | Un-scheduled Visit(s) |
|--|---|--------------------------------------|---|--|---------------------------|--|--------------------------|
| | Visit 5 Week 22 (± 3 days) | Visit 6 Week 30 (± 3 days) | Visit 7 Week 38 EOS/ET ^a (± 3 days) | Week 39 (± 3 days) | Week 40 (± 3 days) | | |
| | Study Drug Dosing | | | Tapered 50% each week. No Study Visit | | | |
| C-SSRS | X | X | X | | | X | X |
| Qualitative Caregiver Behavioral Problems/Improvements Survey | X | X | X | | | | |
| Children’s Sleep Habit Questionnaire | | | X | | | | |
| Pediatric Anxiety Rating Scale-Revised | X | X | X | | | | |
| Daily Study Drug Application | X | X | X | X | X | | |
| Parent/caregiver Completes Daily Skin Irritation Diary ^{f, h} | X | X | X | X | X | X | X |
| Review Patient Skin Irritation Diary | X | X | X | | | X | X |
| Skin Irritation Exam ⁱ | | | X | | | X | X |
| Adverse Event Review | X | X | X | | | X | X |

Table 6 Footnotes - Period 2:

- a. Patients who withdraw prior to Period 2 Week 38 will complete the EOS/ET at Week 38. AED patients will taper study drug for 1 or 2 weeks after the EOS Visit and return on Week 40 or 41 for final discharge from the study, unless they are transitioning to receive drug through Special Access.
- b. Patients will have both weight and height taken at EOS/ET. For patients taking AEDs and returning on Week 40 or 41 to be discharged from the study, a targeted physical examination (heart, lungs, abdomen and extremities) may be performed, if the investigator deems clinically relevant.
- c. Vital signs (including blood pressure, heart rate, respiratory rate, and infrared forehead or oral or tympanic temperature) will be recorded after the patient has been sitting for at least 5 minutes. Vital signs will be assessed at each study visit pre-dose.
- d. A pregnancy test will be completed at Week 38/EOS/ET for all females of childbearing potential. Pregnancy tests can be plasma or urine.

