7.8. End of Study / Early Termination Visit

All patients will complete the EOS/ET Visit assessments at Week 38. Patients not taking AEDs will only have a morning dose of study drug at the Week 38 Visit before discharge from the study. The following will be completed at the EOS/ET Visit:

- Laboratory and urinalysis tests as defined in Section 7.6.15.3.
- Concomitant medication review
- Physical/neurological examination
- Vital signs
- 12-lead ECG
- Pregnancy test (females only)
- Collection and site review of patient Daily Skin Irritation Diary (diary for AED patients will also be collected Week 16 or 17)
- CBD/THC plasma sample drawn
- Valproic acid plasma sample drawn (for patients taking valproate or valproic acid)
- Skin irritation examination
- Adverse event review
- Completion of patient questionnaires and scales – refer to Table 5 and Table 6 in Section 7.7
- Study drug will be applied (last dose for patients not taking AED medication, not applicable to ET patients)

Patients not on AEDs who are prematurely discontinued will complete the early termination procedures at Visit 7 EOS/ET.

Patients taking valproate or valproic acid for treatment of seizures or epilepsy including patients who prematurely discontinue, will taper their current study dose in the following manner beginning at Visit 7 EOS/ET. Should patients taking AEDs at the EOS continue to receive drug through Special Access (if available) they will not taper their dose.

- Participants who weigh 35 kg or less and were receiving 250 mg daily dose of ZYN002, will be reduced to 125 mg daily dose over one week. Only one sachet will be applied each day around the same time in the evening. After the taper, the participants will discontinue from the study at Week 40.
 - If the participant's dose was increased at Week 6 to 500 mg daily dose of ZYN002, the dose will be reduced to 250 mg daily dose over one week with 2 sachets applied each day around the same time in the evening. After the taper, the participants will discontinue from the study at Week 40.

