- Participants who weigh 35 kg or more and were receiving 500 mg daily dose of ZYN002, will be reduced over two weeks. During the first week the dose will be reduced to 125 mg two times a day (applied 12 hours apart) which will make the total daily dose 250 mg. This is one sachet in the morning and one sachet in the evening. During the second week, the dose will decrease to 125 mg daily dose, which means one sachet each day for a week applied each day around the same time in the evening. After the taper, the participants will discontinue from the study at Week 41.

- If the participant's dose was increased at Week 6 to 750 mg daily dose of ZYN002, the dose will be reduced to 375 mg daily dose during the first week with one sachet applied in the morning and 2 sachets applied every evening. During the second week, the dose will decrease to 250 mg daily dose, which means 2 sachets each day for a week applied each day around the same time in the evening. After the taper, the participants will discontinue from the study at Week 41.
- Patients tapering their dose will have all Visit 7 EOS/ET assessments completed.
- At Week 38, patients will have their original dose in the morning and will have their evening dose as their new tapered dose.
- Patients will return at Week 40 or 41 and have the following assessments completed:
 - Concomitant medication review
 - Vital signs
 - Targeted physical exam if investigator deems clinically relevant
 - Pregnancy test (females only)
 - C-SSRS administered
 - Collection and review of Skin Irritation Diary
 - Skin irritation examination
 - Adverse event review

Patients having a skin irritation score > '0' at Week 38 will continue to be followed through Unscheduled Visits until the skin irritation score is recorded as '0' (no erythema).

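### The schedules halve the taper dose every week but the written 750 mg/day taper does not, and the two taper weight bands both include 35 kg

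*Protocol*

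**What the plan says.** **Schedules.** The taper columns of Protocol Table 5 (Weeks 15 and 16) and Table 6 (Weeks 39 and 40) carry one instruction: "Tapered 50% each week. No Study Visit". The SAP repeats it in its own schedules (SAP Section 4.4). Footnote a to each table adds that "AED patients will taper study drug for 1 or 2 weeks after the EOS Visit". Under Table 5 the patient then returns at Week 16 or 17; under Table 6, at Week 40 or 41.

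**Written steps.** Protocol Section 7.8, the Protocol synopsis and the SAP synopsis give the same four tapers, all starting at Visit 7:

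- 35 kg or less on 250 mg/day: "will be reduced to 125 mg daily dose over one week", discharge at Week 40.
- 35 kg or less, raised to 500 mg/day at Week 6: "the dose will be reduced to 250 mg daily dose over one week with 2 sachets applied each day", discharge at Week 40.
- 35 kg or more on 500 mg/day: "Participants who weigh 35 kg or more and were receiving 500 mg daily dose of ZYN002, will be reduced over two weeks". The first week is one sachet twice a day, "which will make the total daily dose 250 mg"; the second is 125 mg/day. Discharge is at Week 41.
- 35 kg or more, raised to 750 mg/day at Week 6: 375 mg/day in the first week, then "During the second week, the dose will decrease to 250 mg daily dose, which means 2 sachets each day for a week". Discharge is at Week 41.

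**Dosing bands.** Sections 7.4 and 9.1 split patients at ≤ 35 kg and > 35 kg. Sections 7.4 and 7.5 leave a dose change after a weight change to the investigator's discretion.

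**The concern.** The taper is an operative dosing instruction for children treated for seizures or epilepsy. It sets the drug supply dispensed (one or two weeks) and the week of the final visit. If the schedule and the written steps disagree, or two weight rules claim the same patient, a site cannot comply with every passage at once, and whatever it does departs from one of them. Protocol Section 13.5 also tabulates adverse events by the dose being taken at onset, so an unclear taper dose blurs that attribution for events in those weeks.

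The schedule heading is not idle. Section 7.8 ties its steps to Visit 7 and to discharge at Week 40 or 41. AED patients who do not qualify for Period 2 taper after Week 14 under Table 5, and for them the heading is the only taper-size instruction attached to their weeks. The Week 6 increase is open to patients with less than 25% improvement, while Period 2 needs at least 35%. Patients on an increased dose, including 750 mg/day, may therefore plausibly be among those who leave at Week 14. The documents do not say how many.

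**Working it through.** **1. Does each written step match the 50% heading?**

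Inputs: the doses in Section 7.8 and the 50% in Tables 5 and 6. Weekly reduction = 1 − (dose this week ÷ dose the week before).

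| Taper rule | Week 1 | Week 2 |
|---|---|---|
| 35 kg or less, 250 mg/day | 1 − 125/250 = 50.0% | none |
| 35 kg or less, raised to 500 mg/day | 1 − 250/500 = 50.0% | none |
| 35 kg or more, 500 mg/day | 1 − 250/500 = 50.0% | 1 − 125/250 = 50.0% |
| 35 kg or more, raised to 750 mg/day | 1 − 375/750 = 50.0% | 1 − 250/375 = 33.3% |

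Five of the six steps reproduce the heading. The exception is week 2 from 750 mg/day.

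Could rounding to whole sachets explain it? A sachet holds 2.98 g × 4.2% = 125.16 mg, nominally 125 mg (Section 9.1). Halving 375 gives 187.5 mg, and 187.5 ÷ 125 = 1.5 sachets. The written 250 mg is 2 sachets. So literal halving cannot be done in whole sachets at this step. That may explain the exception, but no passage says so.

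Could the heading mean 50% of the starting dose removed each week? Then week 2 would be 0 mg in both two-week tapers, and two written steps would fail instead of one. Neither reading fits all six.

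**2. Which written rule applies at each weight?**

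Inputs: the band wording and doses in Section 7.8.

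| Weight and daily dose | 35 kg or less rule | 35 kg or more rule |
|---|---|---|
| 34.9 kg, 500 mg | applies | – |
| 35.0 kg, 250 mg | applies | – |
| 35.0 kg, 500 mg | applies (one week, Week 40) | applies (two weeks, Week 41) |
| 35.1 kg, 500 mg | – | applies |
| 35.1 kg, 250 mg | – | – |

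The third row is the contradiction: the same patient gets two taper lengths and two discharge weeks. The dosing bands do not produce it, because 35.0 kg falls only in ≤ 35.

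**3. Which weight?**

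Weight is measured at Screening, Visit 4 and Visit 7 (Section 7.6.9). Section 7.8 names none of these as governing. Take a child raised to 500 mg/day at Week 6 while at or below 35 kg who is above 35 kg at Visit 7. By the weight used for dosing, the one-week rule applies; by current weight, the two-week rule does. If current weight governs, a child now above 35 kg but left on 250 mg/day matches no written taper (last row), which can happen because the dose change is optional.

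**The case against.** The strongest reply is that a site would not be misled. Section 7.5 sends the reader to Section 7.8, which gives daily doses and sachet counts repeated in both synopses. The table entry is only a column heading, and 1.5 sachets would not be applied in place of a written instruction for 2. Section 7.8 also mentions Week 16 or 17 once, for diary collection, so its authors evidently had Week 14 leavers in mind. At 35.0 kg, the dosing rule starts the patient on 250 mg/day, so 500 mg/day is normally reached through the Week 6 increase, and that is the lower-band sub-bullet. The present-tense weight wording also points to current weight.

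Much of this stands. It makes the likely intention guessable and the practical reach small. It does not remove the conflict: the steps are still tied to Visit 7, the upper-band bullet is not limited to patients who started on 500 mg/day, and the governing weight is left to inference.

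Stronger readings are tempting but unsupported:

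- *The written steps ignore the 50% rule.* Only one of six does.
- *Two tapers from 500 mg/day contradict each other.* Written exposure does differ: 250 × 7 = 1,750 mg, against 250 × 7 + 125 × 7 = 2,625 mg. But tapering by weight is a design choice, and away from 35 kg either rule can be followed. The same holds for the differing last doses (125 or 250 mg/day).
- *The taper is the only dose-reduction rule.* Dose may also be adjusted for weight, and dosing may be suspended for a skin score of 4.
- *Taper-phase safety comparisons are undermined.* None is planned. SAP Sections 8 and 8.1.1 summarise adverse events by period and overall, and the Note to File at the front of the SAP reports a single arm.

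**Conclusion.** The taper instructions contradict each other in two places. First, the schedules require 50% each week, but week 2 from 750 mg/day is a 33.3% reduction. Second, both taper bands include 35 kg, so a 35 kg patient on 500 mg/day is given both one week (Week 40) and two weeks (Week 41). Two omissions widen this: no governing weight is named for a child who crosses 35 kg, and the written steps are not tied to tapers that begin at Week 14.

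The size is modest. About 20 patients are enrolled, and only those on AEDs taper. The documents do not say how many that is, how many reach 750 mg/day, or how many are near 35 kg. No planned efficacy or safety comparison depends on the point. It is a matter of consistent instructions and traceable dosing. The conclusion rests on the text alone and assumes nothing about what sites did.

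**What to change.** Reconcile the taper headings in Protocol Tables 5 and 6 and the SAP schedules with Section 7.8 and the two synopses, so that one set of steps is stated everywhere. Make the taper weight bands non-overlapping and consistent with the dosing bands. State which weight measurement governs the taper, and state explicitly how the steps apply, with their weeks, to patients who taper after Week 14. The steps and doses are for the sponsor to decide; none is proposed here.

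The cost is amendment wording, with no added visit or procedure. The Note to File, effective 16 February 2026, describes data collection in the past tense and says that the Protocol and SAP will not be updated. If the tapers have already been given, the equivalent is a short note to file or a paragraph in the study report listing the taper each affected patient actually received.

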8. SELECTION AND WITHDRAWAL OF PATIENTS

8.1. Patient Inclusion Criteria

Patients must qualify based on meeting all of the inclusion and none of the exclusion criteria to be eligible to enroll.

1. Male or female children and adolescents aged 4 to < 18 years, at the time of Screening.
2. Judged by the Investigator to be in generally good health at Screening based upon the results of a medical history, physical examination, and clinical laboratory test results. Laboratory results outside of the reference range must be documented as not clinically significant by the Investigator.
3. Patients must have a diagnosis of 22qDS confirmed by genetic testing, with or without autistic features.
4. Patients have a CGI-S score of 4 or higher at Screening and Visit 2.
5. Patients must have a severity score on the PARS-R of 10 or higher at Screening and Visit 2.
6. Patients with a history of seizure disorders must currently be receiving treatment with a stable regimen of one or two AEDs, or must be seizure-free for one year if not currently receiving AEDs.
7. If patients are receiving non-pharmacological behavioral and/or dietary interventions, they must be stable for three months prior to Screening.
8. Patients have a body mass index between 12–35 kg / m² (inclusive).
9. Patient has demonstrated stable calcium levels for one year prior to Screening.
10. Females of childbearing potential must have a negative pregnancy test at the Screening Visit and a negative pregnancy test at all designated study visits.
11. Patients and parents/caregivers agree to abide by all study restrictions and comply with all study procedures.
12. Patients and parents/caregivers must be adequately informed of the nature and risks of the study and give written informed consent (and assent if applicable) prior to Screening.
13. Parents/caregiver(s) must provide written consent to assist in study drug administration.
14. In the Investigator's opinion, patients and parents/caregivers are reliable and willing and able to comply with all protocol requirements and procedures.

8.2. Patient Exclusion Criteria

Any of the following is considered criterion for exclusion:

1. Females who are pregnant, nursing, or planning a pregnancy; females of childbearing potential and male patients with a partner of childbearing potential who are unwilling or unable to use an acceptable method of contraception as outlined below for the duration of therapy and for three months after the last dose of study medication.
 - a. Standard acceptable methods of contraception include abstinence or the use of a highly effective method of contraception, including hormonal contraception, diaphragm, cervical cap, vaginal sponge, condom, vasectomy, or intrauterine device.
2. History of significant allergic condition, significant drug-related hypersensitivity, or allergic reaction to any compound or chemical class related to ZYN002 or its excipients.
3. Exposure to any investigational drug or device ≤ 30 days prior to Screening or at any time during the study.
4. Patient has alanine aminotransferase (ALT), aspartate aminotransferase (AST), or total bilirubin levels ≥ 2 times the upper limit of normal (ULN) or has alkaline phosphatase levels ≥ 3 times the ULN as determined from Screening safety laboratories.
5. Use of cannabis or any THC or CBD-containing product within three months of Screening Visit or during the study.
6. Patient has a positive drug screen for sympathomimetic amines (amphetamines (unless prescribed); benzodiazepines; buprenorphine; cannabinoids; methadone; cocaine (metabolites); and opiates; (excludes barbiturates used as AED medication), including ethanol.
7. Patient is using the following AEDs: clobazam, phenobarbital, ethosuximide, felbamate, carbamazepine, phenytoin, or vigabatrin.
8. Patient is using any strong inhibitor/inducer of CYP3A4 or sensitive substrate for CYP3A4 including but not limited to the following medications: midazolam, oral ketoconazole, fluconazole, nefazadone, rifampin, alfentanil, alfuzosin, amiodarone, cyclosporine, dasatinib, docetaxol, eplerenone, ergotamine, everolimus, fentanyl, halofantrine, irinotecan, lapatinib, levomethadyl, lumefantrine, nilotinib, pimozone, quinidine, ranolazine, sirolimus, tacrolimus, temsirolimus, toremifene, tretinoin, vincristine, vinorelbine, St. John's Wort, and grapefruit juice/products.
9. Patient with diagnosis of known genetic disorder, other than 22qDS (i.e. Prader-Willi Syndrome, Angelman Syndrome, Fragile X Syndrome, Rett Syndrome etc.).
10. Patient has diagnosis of DiGeorge or Velocardiofacial syndrome without the presence of 22qDS.
11. Patient has a primary psychiatric diagnosis other than 22qDS or anxiety, including bipolar disorder, psychosis, schizophrenia, post-traumatic stress disorder (PTSD) or major depressive disorder.
12. Patient is on stable treatment of > 6 months of not more than two psychoactive medications at screening or throughout the study (with the exception of one psychoactive medication prescribed for sleep).
13. Patient has an advanced, severe, or unstable disease that may interfere with the study outcome evaluations.
14. Patient is expected to initiate or change pharmacologic or non-pharmacologic

interventions during the course of the study.

15. Patient has an acute or progressive neurological disease, or any psychiatric disorder or severe mental abnormalities that are likely to require changes in drug therapy or interfere with the objectives of the study or ability to adhere to protocol requirements.
16. Patient has a positive result for the presence of HBsAg, HCV, or HIV antibodies.
17. Patients at risk of needing cardiovascular surgical repair within the upcoming 12 months.
18. Patient has unstable cardiovascular disease, such as advanced arteriosclerosis, cardiomyopathy, serious heart rhythm abnormalities, coronary artery disease, cardiac conduction problems, exercise-related cardiac events including syncope and pre-syncope, risk factors for Torsades de pointes (TdP) (e.g., heart failure, hypokalemia, family history of Long QT Syndrome), other serious or other clinically unstable cardiac problems as indicated by history, physical examination or ECG.
19. Any clinically significant condition or abnormal findings at the Screening Visit that would, in the opinion of the Investigator, preclude study participation or interfere with the evaluation of the study medication.
20. Any skin disease or condition, including eczema, psoriasis, melanoma, acne, contact dermatitis, scarring, imperfections, lesions, tattoos, or discoloration, that may affect treatment application, application site assessments, or absorption of the study drug.
21. History of treatment for, or evidence of, drug abuse within the past year.
22. Patient responds “yes” to Question ‘4’ or ‘5’ on the C-SSRS (Children) during Screening or at any time on study.

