8. Patient is using any strong inhibitor/inducer of CYP3A4 or sensitive substrate for CYP3A4 including but not limited to the following medications: midazolam, oral ketoconazole, fluconazole, nefazadone, rifampin, alfentanil, alfuzosin, amiodarone, cyclosporine, dasatinib, docetaxol, eplerenone, ergotamine, everolimus, fentanyl, halofantrine, irinotecan, lapatinib, levomethadyl, lumefantrine, nilotinib, pimozide, quinidine, ranolazine, sirolimus, tacrolimus, temsirolimus, toremifene, tretinoin, vincristine, vinorelbine, St. John's Wort, and grapefruit juice/products.
9. Patient with diagnosis of known genetic disorder, other than 22qDS (i.e. Prader-Willi Syndrome, Angelman Syndrome, Fragile X Syndrome, Rett Syndrome etc.).
10. Patient has diagnosis of DiGeorge or Velocardiofacial syndrome without the presence of 22qDS.
11. Patient has a primary psychiatric diagnosis other than 22qDS or anxiety, including bipolar disorder, psychosis, schizophrenia, post-traumatic stress disorder (PTSD) or major depressive disorder.
12. Patients is on stable treatment of >6 months of not more than two psychoactive medications at screening or throughout the study (with the exception of one psychoactive medication prescribed for sleep).
13. Patient has an advanced, severe, or unstable disease that may interfere with the study outcome evaluations.
14. Patient is expected to initiate or change pharmacologic or non-pharmacologic interventions during the course of the study.
15. Patient has an acute or progressive neurological disease, or any psychiatric disorder or severe mental abnormalities that are likely to require changes in drug therapy or interfere with the objectives of the study or ability to adhere to protocol requirements.
16. Patient has a positive result for the presence of HBsAg, HCV, or HIV antibodies.
17. Patients at risk of needing cardiovascular surgical repair within the upcoming 12 months.

18. Patient has unstable cardiovascular disease, such as advanced arteriosclerosis, cardiomyopathy, serious heart rhythm abnormalities, coronary artery disease, cardiac conduction problems, exercise-related cardiac events including syncope and pre-syncope, risk factors for Torsades de pointes (TdP) (e.g., heart failure, hypokalemia, family history of Long QT Syndrome), other serious or other clinically unstable cardiac problems as indicated by history, physical examination, or ECG.

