9.2.1. Concomitant Medications Allowed

Patients may take hormonal contraception and AEDs (not in the exclusion criteria) during study participation.

Patients on a stable treatment of >6 months are allowed two psychoactive medications at screening or throughout the study.

For the purposes of the protocol, the following sedative medications, when used as a single, bedtime dose – need not be considered one of the two allowed psychotropic medications:

- Clonidine
- Guanfacine
- Melatonin
- Diphenhydramine or other sedating antihistamine medications

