2. History of significant allergic condition, significant drug-related hypersensitivity, or allergic reaction to any compound or chemical class related to ZYN002 or its excipients.
3. Exposure to any investigational drug or device ≤ 30 days prior to Screening or at any time during the study.
4. Patient has alanine aminotransferase (ALT), aspartate aminotransferase (AST), or total bilirubin levels ≥ 2 times the upper limit of normal (ULN) or has alkaline phosphatase levels ≥ 3 times the ULN as determined from Screening safety laboratories.
5. Use of cannabis or any THC or CBD-containing product within three months of Screening Visit or during the study.
6. Patient has a positive drug screen for sympathomimetic amines (amphetamines (unless prescribed); benzodiazepines; buprenorphine; cannabinoids; methadone; cocaine (metabolites); and opiates; (excludes barbiturates used as AED medication), including ethanol.
7. Patient is using the following AEDs: clobazam, phenobarbital, ethosuximide, felbamate, carbamazepine, phenytoin or vigabatrin.
8. Patient is using any strong inhibitor/inducer of CYP3A4 or sensitive substrate for CYP3A4 including but not limited to the following medications: midazolam, oral ketoconazole, fluconazole, nefazadone, rifampin, alfentanil, alfuzosin, amiodarone, cyclosporine, dasatinib, docetaxol, eplerenone, ergotamine, everolimus, fentanyl, halofantrine, irinotecan, lapatinib, levomethadyl, lumefantrine, nilotinib, pimozone, quinidine, ranolazine, sirolimus, tacrolimus, temsirolimus, toremifene, tretinoin, vincristine, vinorelbine, St. John's Wort, and grapefruit juice/products.
9. Patient with diagnosis of known genetic disorder, other than 22qDS (i.e. Prader-Willi Syndrome, Angelman Syndrome, Fragile X Syndrome, Rett Syndrome etc.).
10. Patient has diagnosis of DiGeorge or Velocardiofacial syndrome without the presence of 22qDS.
11. Patient has a primary psychiatric diagnosis other than 22qDS or anxiety, including bipolar disorder, psychosis, schizophrenia, post-traumatic stress disorder (PTSD) or major depressive disorder.
12. Patients is on stable treatment of >6 months of not more than two psychoactive medications at screening or throughout the study (with the exception of one psychoactive medication prescribed for sleep).
13. Patient has an advanced, severe, or unstable disease that may interfere with the study outcome evaluations.

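### Exclusion criterion 12 shuts out patients whom Section 9.2.1 allows, and no eligibility criterion then limits the number of psychoactive drugs or requires stability before screening

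*Protocol*

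**What the plan says.** Section 8.1 of the protocol sets the enrolment rule: "Patients must qualify based on meeting all of the inclusion and none of the exclusion criteria to be eligible to enroll". Section 8.2 opens its list with "Any of the following is considered criterion for exclusion", and item 12 of that list reads "Patient is on stable treatment of > 6 months of not more than two psychoactive medications at screening or throughout the study", followed by a parenthesis, "with the exception of one psychoactive medication prescribed for sleep".

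The protocol synopsis repeats the item almost word for word ("Patients is on stable treatment of >6 months of not more than two psychoactive medications at screening or throughout the study"), and so does the synopsis at the front of the SAP ("Patients is on stable treatment of >6 months of not more than two psychoactive medications at screening" and onward). SAP Section 10 reports no changes from the protocol.

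Section 9.2.1, on permitted concomitant medication, says "Patients on a stable treatment of >6 months are allowed two psychoactive medications at screening or throughout the study". It then names several sedatives which, given as a single dose at bedtime, "need not be considered one of the two allowed psychotropic medications".

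**The concern.** Item 12 describes an acceptable state but sits in a list of unacceptable ones. Sections 8.2 and 9.2.1 therefore give opposite answers for the same child.

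This matters because the study has no control arm. Efficacy rests on change within patients, and the SAP plans t-tests of change from baseline against zero for the ABC-C subscales (Section 6.7.1) and for CGI-S (Section 6.7.2). A psychoactive drug started or altered shortly before Day 1 can move these same behavioural ratings, and nothing in the design separates that movement from an effect of ZYN002. A stable background regimen at entry is one of the few protections available, and item 12 is the only eligibility criterion that mentions how many psychoactive drugs a patient takes or for how long.

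The consequence depends on which section a site followed. A site following 8.2 literally turns away patients on one or two stable drugs. A site following 9.2.1 enrols them, and each then breaches the written eligibility rule. Sites may have differed.

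**Working it through.** No figure in the plan is at issue, so the check is logical: apply the text to each type of patient.

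| Patient at screening | Exclusion 12 as written | Section 9.2.1 | Other eligibility criteria |
|---|---|---|---|
| One or two psychoactive drugs, stable for more than 6 months | Excluded | Allowed | No separate bar |
| Three or more psychoactive drugs | Not caught | Limit of two implied | No limit on number |
| One or two drugs, stable for 6 months or less | Not caught | Outside the stated permission | Caught only in the circumstances below |
| No psychoactive drug | Not affected on the natural reading | Not addressed | No bar |

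The first row is a direct contradiction. Rows two and three show what is left uncovered. The criteria that might cover it are these:

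- **Exclusion 14** concerns interventions expected to be started or changed during the study. It does not look back before screening and sets no limit on number. Screening runs from Day -28 to Day -8 (Table 4), so a drug begun between Screening and Day 1 is arguably caught. One begun shortly before Screening is not.
- **Exclusion 15** applies only where a neurological or psychiatric disorder is likely to need changed drug therapy or to interfere with the study.
- **Exclusions 13 and 19** cover unstable disease and conditions that, in the investigator's judgement, interfere with evaluation. Both turn on the patient's condition, not on the regimen.
- **Exclusions 7 and 8** bar named anti-epileptic drugs and drugs acting on or cleared by CYP3A4, whatever their duration.
- **Inclusions 6 and 7** ask for a stable regimen of anti-epileptic drugs and for three months of stability in non-drug and dietary interventions. Neither covers psychoactive drugs in general.
- **Section 9.2.1** implies a limit of two but stands outside the eligibility list, and Section 9.2.2 lets the investigator approve other medication in advance.

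So some patients on unstable regimens are still removed, but no eligibility criterion sets a pre-screening stability period or a maximum number.

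There is a second mismatch. Item 12 excepts one psychoactive drug prescribed for sleep, whichever it is. Section 9.2.1 exempts listed sedatives at a single bedtime dose and does not say that only one may be left uncounted. A prescribed sleep drug that is not on the list is excepted by the first and counted by the second.

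**The case against.** The best reply is that this is a drafting slip with a recoverable intent. Section 9.2.1 states the permission affirmatively, and exclusion 6 tolerates a positive amphetamine screen when the drug is prescribed, so the protocol plainly expects some children on psychoactive treatment. Sites may well have worked to 9.2.1. No analysis set depends on the criterion: the Safety, mITT and PK sets are defined by dosing and post-baseline data, and there is no per-protocol set. Prior and concomitant medications are summarised and listed, with start and stop dates taken from the CRF, so a reader of the listings could find recent starts.

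Most of that stands, and it limits the harm. It does not remove the contradiction: a patient must meet none of the exclusions, so enrolment under 9.2.1 is still a breach of 8.2. Nor do the medication summaries classify regimens by stability; SAP Section 6.2.3 sorts them only by timing relative to first dose and study treatment.

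Three stronger readings are tempting, and the documents do not support them.

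- A reader might infer that the plan freely admits patients on any number of drugs or on unstable regimens. Exclusions 13, 14, 15 and 19 and the implied limit in 9.2.1 still remove some of them.
- A reader might estimate how many of the roughly 20 patients are affected from the diagnosis rates in Section 5.1 (ADHD, ASD and anxiety at about 40% each). Those are rates of diagnosis, not of drug use. Table 3 of the protocol also gives much lower figures for autism (14%) and generalized anxiety (8%).
- A reader might infer that Listings 16.7 and 16.8 would flag the wrong patients. The SAP gives only their titles, with no rule for deriving them.

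**Conclusion.** Wrong as written. Exclusion 12 reverses the status of one class of patients relative to Section 9.2.1, and the faulty wording stands in three places: Protocol 8.2, the protocol synopsis and the SAP synopsis. No current copy corrects it. The gap that follows is specific: the eligibility list contains no limit on the number of psychoactive drugs and no pre-screening stability requirement for them.

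The contradiction rests on the text alone and needs no assumption about patient numbers. The risk of bias does rest on assumptions: that some enrolled patients had recently changed psychoactive treatment, and that the partial safeguards did not stop them. The documents do not show how often that happened, so no size is given. Nor do they show which section the sites applied.

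**What to change.** Reconcile Section 8.2 item 12 with Section 9.2.1. Which medication rule should apply is for the sponsor to decide; the two sections must say the same thing.

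If 9.2.1 is the intent, restate the item conditionally, on the model of inclusion 7: if a patient is receiving psychoactive medication, then the stated conditions on number and duration apply. Moving the sentence unchanged to the inclusion list would not do, because every inclusion criterion must be met and a patient on no psychoactive drug would fail it. Excluding everyone who does not satisfy 9.2.1 carries the same risk, since an untreated patient is not on stable treatment.

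At the same time, align the sleep-medication exception between the two sections, correct both synopses, and assess eligibility deviations against the reconciled wording. The Note to File at the front of the SAP, written about dose grouping, says that the protocol and SAP will not be updated. A short clarification memo would serve instead, and should record which rule the sites applied.

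The cost is one sentence in three places, or one memo, plus the wording of the sleep exception. Visits, data collection and sample size are unaffected.
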